6 SUBJECT DISPOSITION

Subject disposition will be summarized for all screened subjects. Randomized subjects who complete the study or discontinue early from the study will be summarized by treatment group and overall subjects. The summary of subject disposition by discontinuation reason will also be presented. Within a treatment group or the overall summary, all percentages will be based on the number of randomized subjects within the treatment group or all randomized subjects, respectively.

A listing of study completion will be provided for all randomized subjects. A separate listing will be provided for screen failures with the reason for screen failure.

7 ANALYSIS POPULATION

7.1 Randomized Population

Randomized subjects will include all subjects whose date of randomization is not missing. The study population summary will be performed on the randomized subjects.

The randomized population will be used as supportive analysis for the primary and key secondary efficacy endpoints. Subjects will be analyzed based on the treatment to which they were randomized.

7.2 Safety Population

The safety population includes all subjects randomized either received study treatment [timrepigene emparvovec] or a post-randomization study visit (Telephone Call or a site visit) [Control].

Subjects will be analyzed according to their actual treatment received.

The safety population will be used for all safety analyses.

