9.4 Vitrectomy Procedure and Injection of AAV2-REP1

Injection of AAV2-REP1 is to be performed by an appropriately qualified and experienced retinal surgeon. All surgeons must have completed all study-specific surgical training and obtained certification by NightstaRx to perform the study procedure, before treating a study participant.

Due to the complexity and unpredictability of detaching the retina in end-stage CHM, in which the retina and choroid are extremely thin and fused in places, a modification to the technique of sub-retinal gene therapy has been developed. This involves performing the vector delivery in 2 steps after vitrectomy. An advantage of a 2-step procedure is that any unexpected complications of retinal detachment can be managed conservatively, minimising concerns about the vector escaping into the vitreous. Further, the injection could be deferred until a later date if, for instance, a macular hole was created which required treatment with gas. Also, since the volume of fluid required to detach the fovea is variable, by removing the vector from the first step, a precise consistent dose in terms of genome particles can still be applied into the sub-retinal space.

Initially, subjects will undergo a standard vitrectomy and detachment of the posterior hyaloid (Figure 2). All surgery will be conducted using the standard BIOM vitrectomy system. A 23-gauge sutured approach is usually favoured to avoid any potential risks of wound leakage. The retina will be detached with 100-500 μ L of balanced salt solution (BSS) injected through a 41-gauge sub-retinal cannula connected to a vitreous injection set (this is the first step of the 2-step procedure).

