13.3.3 Safety Population

The Safety population includes all subjects randomised and who attended Visit 2 (either received study treatment [AAV2-REP1] or a study visit Telephone Call [Control]).

Subjects will be analysed according to their actual treatment received.

The Safety population will be used for all safety analyses.

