5 GENERAL ASPECTS FOR STATISTICAL ANALYSIS

5.1 General Methods

All analyses and summaries will be produced using SAS® version 9.4 (or higher).

For descriptive summary statistics, the efficacy and safety data will be summarized and displayed by treatment groups (Control, Low Dose, High Dose) and visits (Baseline, Month 1, 4, 8, 12, and End of Study).

Summary statistics will be presented for continuous variables, by way of number of subjects, mean, standard deviation (SD), median, first and third quartiles (Q1 and Q3, respectively), 5th and 95th percentiles (P05 and P95, respectively), minimum and maximum. Where specified, the 95% Confidence Interval (CI) of the mean will be calculated. Summary statistics will be presented where appropriate by treatment and nominal visit with an additional entry for the end of study.

For categorical variables (including binary variables), counts and percentages will be presented. Where specified, the 95% 2-sided CI for proportions will be calculated.

The listings, except the listing for screen failures, will include all randomized subjects in the database. In general, the subject listings will be sorted by treatment group, subject number, eye (starting with the study eye) and assessment date (and time, if applicable).

Data for unscheduled assessments will be included when calculating baseline values, selecting worst result for shift analyses, and for summary of normal/abnormal values. The safety summary of observed and change from baseline data will be performed by nominal (i.e., scheduled) visits. Unscheduled visits will be included in the analysis of End of Study, i.e., the last available non-missing treatment endpoint.

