11.1 Adverse Events

Treatment-emergent adverse events (TEAEs) are defined as adverse events starting on or after the day of the surgery (or, for control subjects, Visit 2, Day 0). A pre-existing event that worsens in severity after Day 0 is treated as a new TEAE with date of onset set to the date of the increased severity. Summary tables will include TEAEs only. TEAEs will be summarized by eye (study eye vs non-study eye) for ocular events, by treatment (low dose, high dose and untreated control) and overall. Non-treatment emergent AEs will be listed only.

An ocular event is an event where the site of the event is reported as both eyes (OU), right eye (OD) or left eye (OS).

Proportion of subjects reporting an event will be calculated based on the number of subjects in the corresponding treatment group. The 95% CI will be calculated using the Clopper-Pearson method.

The number and percentage of subjects reporting any event, any non-ocular event, any ocular event, any ocular event in the study eye and any ocular event in the non-study eye will be summarized.

The summary of overall AEs (or SAEs) will be limited to TEAEs. All AEs will be coded using Medical Dictionary for Regulatory Activities (MedDRA) version 21.1 or higher.

An overall summary table of TEAE by treatment will be provided for the following categories:

- Number and percentage of subjects with a TEAE
- Number and percentage of subjects with a treatment-related TEAE
- Number and percentage of subjects with a serious TEAE
- Number and percentage of subjects with a treatment-related serious TEAE
- Number and percentage of subjects with a TEAE leading to death
- Number and percentage of subjects who discontinued due to a TEAE
- Number and percentage of subjects with a TEAE by severity
- Number and percentage of subjects with a TEAE by outcome
- Number and percentage of subjects with a TEAE by action taken

Adverse events will be summarized by treatment group and overall for subjects in the safety population. The following summaries of TEAEs will be provided:

- TEAEs by SOC and PT
- TEAEs by SOC and PT reported in \geq 5% in any treatment group

Biogen /	NightstaRx,	Ltd
RIIR111		

- TEAEs by SOC, PT, and maximum severity (missing severity, if any, will be counted as severe).
- Treatment-related (study drug or study procedure) TEAEs by SOC and PT
- Study procedure-related TEAEs by SOC and PT
- Study drug-related TEAEs by SOC and PT
- Serious TEAEs by SOC and PT

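### Treated-arm subjects enter the safety population only if they received the vector, so a subject operated on but never injected would leave every safety summary table

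*SAP*

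**What the plan says.** **Entry to the safety population.** SAP 7.2 reads: "The safety population includes all subjects randomized either received study treatment [timrepigene emparvovec] or a post-randomization study visit (Telephone Call or a site visit", with the visit route tagged for Control. It thus admits those who received the vector, or Control subjects with a telephone or site contact after randomisation. Protocol 13.3.3 opens with attendance at Visit 2 and then qualifies it in parentheses: "either received study treatment [AAV2-REP1] or a study visit Telephone Call [Control".

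**Grouping and use.** SAP 7.2 adds: "Subjects will be analyzed according to their actual treatment received". SAP 5.1 has the data "displayed by treatment groups (Control, Low Dose, High Dose", so no group is provided for surgery without vector. SAP 7.2 and SAP 11 use this population for all safety analyses.

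**The operation.** Protocol 9.4 places vitrectomy and detachment of the retina with balanced salt solution before the vector step. It says that "the injection could be deferred until a later date if, for instance, a macular hole was created". Protocol 5.4 gives the same reason for splitting the procedure: surgical complications can be dealt with before vector is applied. Protocol 8.3 lets a subject withdraw at any time.

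**Events to be tabulated.** SAP 11.1 states: "Treatment-emergent adverse events (TEAEs) are defined as adverse events starting on or after the day of the surgery". It also plans separate tables of procedure-related events, serious and overall.

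**The concern.** The SAP sets out to measure harm from the procedure as well as from the drug. It starts the treatment-emergent window at surgery and plans procedure-related tables, yet the population for those tables requires the vector. A treated-arm subject whose surgery stops after the detachment step, and who is never injected, has been exposed to general anaesthesia, vitrectomy and an induced detachment, but no entry route fits him.

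Such an omission would not be random. The subject is left out because a complication stopped the injection, and that complication is the kind of event the tables should count. Protocol 5.4 includes retinal tears, holes and breaks, macular hole and persistent detachment in its list of procedural risks. A Control subject, by contrast, qualifies with one telephone call. Safety is descriptive in this trial, so the rates in the summary tables are what most readers will take away.

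**Working it through.** The plan states no figure on this point, so the check is first a reading of the text and then an illustration of scale.

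**1. Which route fits?** Take a subject randomised to a dose arm who has vitrectomy and detachment, develops a macular hole, has the injection deferred and then withdraws.

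- SAP 7.2, vector route: not met.
- SAP 7.2, visit route: tagged for Control, and he was not randomised to Control.
- Protocol 13.3.3: he attended Visit 2, but the parenthesis limits treated subjects to those who received AAV2-REP1. It is less explicit than the SAP, but its natural reading is the same.

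He is therefore outside the safety population. A subject whose injection is deferred and later given meets the vector route and is included.

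**2. Direction of the bias.** Let N be the subjects operated on, k those never injected because of a complication, and m the subjects with that complication among those injected.

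- Rate among all operated: (m + k)/N
- Rate as tabulated: m/(N − k)
- The first exceeds the second when (m + k)(N − k) > mN, that is, when k(N − m − k) > 0. This holds whenever k is at least 1 and some injected subject is free of the event.

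**3. Scale.** Planned operations (SAP 3.6): 64 + 32 = 96. The values of k are assumptions. The first illustration also assumes m = 0. Intervals are Clopper-Pearson, the method SAP 11.1 names for event proportions. For x = 0 the upper limit is 1 − 0.025^(1/n); at n = 95 this is 3.8%.

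| k (assumed) | As tabulated | All operated |
|---|---|---|
| 1 | 0/95, upper limit 3.8% | 1/96 = 1.0% (0.03 to 5.7) |
| 2 | 0/94, upper limit 3.8% | 2/96 = 2.1% (0.25 to 7.3) |
| 4 | 0/92, upper limit 3.9% | 4/96 = 4.2% (1.2 to 10.3) |

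The SAP displays doses separately. One such subject in the high-dose arm gives 0/63 (upper limit 5.7%) instead of 1/64 = 1.6% (0.04 to 8.4). If m = 4 in that arm, one such subject changes the rate from 5/64 = 7.8% to 4/63 = 6.3%.

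**4. Chance that the case arises.** The documents give no rate. If a proportion r of 96 operations ended without injection, the chance of at least one is 1 − (1 − r)^96. For assumed r of 1%, 2% and 5% this is 62%, 86% and 99%.

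**5. The date anchor.** A deferred and later completed injection means two operations. SAP 11.1 counts from the day of surgery, SAP 5.3 counts study days from the date of treatment, and Protocol 7.1 sets Day 0 as the actual date of surgery. None says which date applies when there are two.

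**The case against.** The strongest reply is that the case is hypothetical. Protocol 9.4 speaks of deferral, not cancellation, and a subject injected later is included. The one count in the documents, in the protocol's summary of changes, leaves nobody over: 51 treated + 29 controls + 3 discontinued before Visit 2 = 83 randomised. That stands as a limit on the claim. The count is interim and does not define 'treated', so it does not rule such cases out, but the bias must be stated conditionally.

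Second, the events are not lost. Adverse events are collected from consent (Protocol 12.3.2), serious ones go to the sponsor within 24 hours (12.3.4), a monitoring committee reviews accruing data (12.3.6), listings cover all randomised subjects (SAP 5.1), and disposition uses randomised denominators (SAP 6). This also stands. Listings, however, give no rate, denominator or comparison between arms.

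Third, the illustration in which no injected subject has the event is a worst case, and its intervals overlap heavily. True; the example with m = 4 relaxes it, and the direction does not depend on it.

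A reader might also infer that such a subject would be tabulated under Control, because he had a site visit and his actual treatment was not the vector. The documents do not support that. The visit route carries the Control tag, and the protocol synopsis defines the reference condition as having neither study drug nor surgery. Exclusion is the natural reading.

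Likewise, a reader might infer that the first operation's complication would count as non-treatment-emergent once a second operation takes place. SAP 11.1 refers to surgery, not injection, and the first operation is surgery, so on a plain reading its complication counts. The text needs only to say so.

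**Conclusion.** The point holds as a gap in the definition. SAP 7.2, and on its natural reading Protocol 13.3.3, has no entry route for a treated-arm subject who was operated on but never injected, although the protocol foresees the step that leads there. Any such case lowers the reported procedural complication rates in the treated arms and removes the subject from the procedure-related tables of SAP 11.1. Under the stated assumptions the understatement in the pooled treated arms is about 1 percentage point for one subject and about 4 for four.

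The size in this trial is unknown. The documents neither give a frequency nor report a case, so they do not show that the reported rates are in fact biased. No efficacy result is affected.

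**What to change.** In SAP 7.2 and Protocol 13.3.3, define the safety population for the treated arms as all randomised subjects in whom the study surgical procedure was started, whether or not vector was injected. Keep the Control route as it is.

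State how subjects with surgery but no vector are displayed: under their randomised dose arm with a flag, or as a separate 'surgery, no vector' group, and never under Control. The first option needs a stated exception to the as-treated rule in SAP 7.2.

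In SAP 11.1, state that the day of surgery means the first study operation when there is more than one.

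The cost is wording in both documents and one flag in the analysis data. No new data are needed: peri-operative events already go to the eCRF (Protocol 9.4), and so does the quantity injected (Protocol 9.9). The small downside is that a few subjects in the surgical-arm tables will not have received vector, which the flag shows. The rule should be settled before database lock, so that placement is not decided case by case once events are known.

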7.3 Intent-To-Treat Population

The Intent-to-Treat (ITT) population is defined as all subjects who are randomized, receive the study treatment (or the phone call for those in the untreated control group), and have at least one post-treatment BCVA measurement.

The ITT population will be used for the efficacy, quality of life, and

The primary population for efficacy analysis is the ITT population. Subjects will be analyzed based on the treatment to which they were randomized.

7.4 Per Protocol Population

The Per Protocol (PP) population is a subset of the ITT population, whereby subjects with major protocol deviations that may affect substantially the results of the efficacy endpoints, are excluded. Subjects will be analyzed by randomized treatment. The definition of PP population is same as stated in the protocol, but an erratum of "actual treatment" is corrected in this document.

Biogen / NightstaRx,	Ltd
BIIB111	

The determination of the major protocol deviations, and therefore the composition of the PP population, will be made prior to unmasking and will be documented and included in the analysis data.

The PP population will be used to analyze the primary and key secondary efficacy endpoints.

7.5 Immunogenicity Population

The Immunogenicity population will include all subjects from the safety population with at least one post-surgery sample evaluable for immunogenicity. The Immunogenicity population will be used for the immunogenicity analyses.

A summary table will be provided which contains the number (%) of subjects with at least one protocol deviation and the number (%) of subjects in each category for each study arm. The table will also summarize the number (%) of subjects with a major protocol deviation and the number (%) of subjects with a major protocol deviation in each category. The table will also present the summary statistics for important protocol deviations. All protocol deviations will be listed.

9 DEMOGRAPHIC AND OTHER BASELINE CHARACTERISTICS

9.1 Demographic and Other Baseline Characteristics

Demographics (sex, race, ethnicity, age [in years], age group [\leq 50 and > 50 years, \leq 60 and > 60 years, \leq median and > median years], baseline weight [kg]) will be summarized for the safety and ITT populations by treatment group and overall subjects. Sex, race, age group, and ethnicity will be summarized using summary statistics for categorical variables. Age and baseline weight will be summarized using summary statistics for continuous variables.

Age is calculated as (Informed Consent date – date of birth + 1)/365.25 and presented to 1 decimal place. No rounding will be carried out prior to summarizing age. Where only the year of birth is reported as per local regulations, the date of birth will be assigned the value 30JUNYYYY.

A listing of demographic data will be provided for all randomized subjects.

9.2 Medical and Ocular History

9.2.1 Medical History

Medical history will be coded using the Medical Dictionary for Regulatory Activities (MedDRA) Version 21.1 or higher. The number and percentage of subjects under each history term, coded by system organ class (SOC) and preferred term (PT), will be summarized by treatment. All percentages will be based on the number of subjects in the safety population within each treatment group. If a subject had a medical history term more than once, the subject will be counted only once under any given SOC or PT.

A listing of medical history will be provided for all randomized subjects.

9.2.2 Ocular History

Ocular History will be summarized by treatment and eye, by SOC and PT, for the safety population.

A listing of ocular history will be provided for all randomized subjects.

9.3 Prior and Concomitant Medications

All medications will be coded using the World Health Organization drug dictionary (WHODRUG) version March 1, 2018 or higher.

Incidence of prior and concomitant medication will be presented by treatment, Anatomical Therapeutic Chemical (ATC) Level 4 and PT for the safety population. Ocular medication will also be presented by eye (study eye and non-study eye).

Prior medications are those that start and stop before exposure to treatment; for control subjects, prior medications are defined as those with start and stop prior to Visit 2 (Day 0). Concomitant medications are all medications taken during the study period, including those started before but ongoing at the time of the injection (or Visit 2, Day 0 in the case of control subjects).

Imputation rules for partial dates are presented in Appendix 3. CONFIDENTIAL

Biogen / NightstaRx, Ltd	
BIIB111	

A subject with more than one occurrence of the same medication in a particular ATC class will be counted only once in the total of those reporting medications in that particular ATC class.

Corticosteroid Treatment/Tapering will be summarized and listed separately.

9.4 Treatment Exposure

As the treatment consists of a single injection, the exposure to study medication will not be summarized.

10 EFFICACY ANALYSIS

10.1 Primary Endpoint

The primary endpoint will be calculated as the proportion of subjects with $a \ge 15$ -letter increase from baseline in BCVA at the Month 12 visit. If a subject had BCVA missing at Month 12, the primary endpoint of the subject will be imputed as a failure.

The primary endpoint will be summarized using the summary statistics for categorical data including the 95% CI. The 95% CI for the difference in proportions will be computed using the method of Miettinen and Nurminen.

The primary endpoint will be compared between study arms (high dose vs control, low dose vs control) using the Fisher's Exact test. The primary approach will be the unstratified analysis, and a supportive analysis will be conducted with the Cochran-Mantel-Haenszel approach by stratifying by surgical group. As Fisher's Exact test is overly conservative when the number of events is low, a supportive analysis will be conducted using Fisher's Exact-Boschloo test with a Berger-Boos correction of beta=0.001 (Berger 1994). To maintain the test at 0.05 two-sided level, the reported p-value will be 2 times the one-sided p-value from the Fisher's Exact-Boschloo test.

The primary analysis of the primary endpoint will be based on the ITT population, and supportive analyses will be performed based on the PP population and the randomization population. Knowing the patients at site **and** who had BCVA below 34 ETDRS letters at Month 12 for study eye, if any, will not be the responders of subjects with a \geq 15-letter improvement from Baseline in BCVA at Month 12, these subjects with minor protocol deviation will be included in the supportive analysis based on the PP population (see background information for site **and** in Section 8).

Let p_{high} , p_{low} , and p_{cont} represent proportions of subjects with an improvement (≥ 15 -letter) from baseline in BCVA at Month 12 for treatments of high dose and low dose, and control group, respectively.

The following 2 hypotheses will be tested to compare the proportions between each treatment group (high dose or low dose) and control group at Month 12:

- High dose treatment versus control:
 - $\circ \quad H_{01}: p_{high} = p_{cont} versus H_{11}: p_{high} \neq p_{cont}$
- Low dose treatment versus control:
 - $\circ \quad H_{02}: p_{low} = p_{cont} versus H_{12}: p_{low} \neq p_{cont}$

Additional supportive analysis will be conducted by comparing the study eyes vs. the fellow eyes (i.e., contralateral control) within the low dose and the high dose treatment groups. The study eye will be compared to the fellow eye at the Month 12 visit using the paired McNemar test.

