3 OVERVIEW OF STUDY DESIGN

3.1 Discussion of Study Design

This is an outcomes-assessor masked, prospective, randomized, parallel- controlled group, multi-center, global, interventional study. The study consists of 8 visits with a 12-month evaluation period (Figure 1). During the Screening/Baseline Period, each subject will be assessed for eligibility. If a subject has only 1 eligible eye, that eye will be designated as the "study eye" and the subject's other (non-eligible) eye will be designated as the "fellow eye." If a subject has 2 eligible eyes, the selection of the "study eye" will be made on clinical grounds and will generally be the worse eye affected.

For eligible subjects, a study eye will be assigned, and the subjects will be randomized in a 2:1:2 ratio to receive either timrepigene emparvovec high dose $(1.0 \times 10^{11} \text{ viral genomes [vg]})$, timrepigene emparvovec low dose $(1.0 \times 10^{10} \text{ vg})$ or to enter the untreated Control group. Once a subject has been randomized, a change in "study eye" designation is not permitted.

At the time of randomization, a projected surgical date should be defined for each subject. For each subject randomized to the control group, this projected surgical date (+/-1 day) should remain the Day 0 (Visit 2) date. For each subject randomized to a treated group, Day 0 (Visit 2) will be the actual date of surgery. The Screening / Baseline period must occur within 8 weeks prior to dosing (Week 2, Day 0).

Study data will be collected for both eyes of each subject.

Since timrepigene emparvovec treatment requires an invasive surgical procedure under general anesthesia, the sponsor, investigator and the subject will be unmasked to the study procedure (i.e. vitrectomy and sub-retinal injection), however within the treated groups, the sponsor, investigator and subject will be masked to the assigned dose $(1.0 \times 10^{11} \text{ vg or } 1.0 \times 10^{10} \text{ vg})$. To further minimize the potential bias of the treated and untreated eye evaluations, all subjective ophthalmic assessments from the Screening/Baseline period (Visit 1) and from Month 1 (Visit 5) onwards, will be conducted by a masked assessor.

Figure 1Overall Study Schematic

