Additional supportive analysis will be conducted by comparing the study eyes vs. the fellow eyes (i.e., contralateral control) within the low dose and the high dose treatment groups. The binary efficacy endpoints will be analyzed at the Month 12 visit using the paired McNemar test. Change from baseline in BCVA at Month 12 will be compared between the study eye and the fellow eye using the linear mixed model where the two eyes are considered correlated within each patient. The model will contain the variables for baseline BCVA, treatment groups (low dose and high dose), surgical group, eye (study eye vs fellow eye) and the treatment*eye interaction, where the eye variable acts as the repeat variable. (See sample SAS code in Appendix 5).

	Key Secondary Endpoint	Statistical Method
1	Change from Baseline in BCVA at Month 12 measured by the ETDRS chart	ANCOVA
2	Proportion of subjects with a ≥10-letter improvement from Baseline in BCVA at Month 12 measured by the ETDRS chart	Fisher's Exact Test; Fisher's Exact-Boschloo test with a Berger-Boos correction of beta=0.001; CMH Approach
3	Proportion of subjects with no decrease from Baseline in BCVA or a decrease from Baseline in BCVA of <5 ETDRS letters at Month 12 measured by the ETDRS chart	Fisher's Exact Test; Fisher's Exact-Boschloo test with a Berger-Boos correction of beta=0.001; CMH Approach

Tabla 1	Statistical Tests	for Vor	Secondamy	Efficient	Endnointe
Table 1	Statistical Lesis	IUI KEY	Secondary	Efficacy	Enapoints

Biogen / NightstaRy	x, Ltd
BIIB111	

Abbreviations: BCVA= best corrected visual acuity, CHM= choroideremia, ETDRS=Early Treatment of Diabetic Retinopathy Study

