14.4.2 Binary endpoint

/*** compute the proportion difference and the corresponding standard error between the treatment groups (i.e. high dose vs. placebo, low dose vs. placebo) for each imputed dataset. Use Rubin's Rule to combine the results ***/

```
PROC MIANALYZE data=propest;
modeleffects prop_diff;
stderr se_diff;
ods output parameterestimates = PARMS;
run;
```

14.5 Appendix 5: Linear Mixed Model for Study Eye vs Fellow Eye Comparison – Sample SAS Code

PROC MIXED DATA=dset; /* assumes data presented in rows */ CLASS trt eye subject; /* be careful of the sequences of the variable here */ /* see notes later */ MODEL var_chg= eye trt eye*trt var bl/ DDFM=KENWARDROGER; REPEATED eye / SUBJECT=subject TYPE=UN R RCORR RI; LSMEANS eye*trt; ESTIMATE 'high dose: study eye vs fellow eye' eye 1 -1 eye*trt 1 -1 0 0 0 0; ESTIMATE 'low dose: study eye vs fellow eye' eye 1 -1 eye*trt 0 0 1 -1 0 0; ESTIMATE 'control: study eye vs fellow eye' eye 1 -1 eye*trt 0 0 0 0 1 -1; /* the variable 'eye' indicates whether the data are study eye or fellow eye */ /* 1 is associated to the study eye data */ /* -1 is associated to the fellow eye data */ /* treatment is coded as 1-high dose, 2-low dose, 0-control */ /* note the sequence of variables in the CLASS statement is very tricky */ $/\star$ in order for the ESTIMATE statement to work correctly: /* if it appears in CLASS statement as 'eye trt subject', then the ESTIMATE */ */ /* statement has to be, for example, /* ESTIMATE 'high dose:study eye vs fellow eye' eye 1 -1 eye*trt 1 0 0 -1 0 0; */ /* When interaction term is added, this statement must be modified

RUN;

*/

*/

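### The supportive study-eye v fellow-eye analyses are described within the treated arms only, although the two eyes are not exchangeable and no contrast against the control arm is planned

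*SAP*

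**What the plan says.** SAP 10.1 adds a supportive analysis of the primary endpoint, "comparing the study eyes vs. the fellow eyes (i.e., contralateral control) within the low dose and the high dose treatment groups", and specifies: "The study eye will be compared to the fellow eye at the Month 12 visit using the paired McNemar test". SAP 10.2 repeats this for the key secondary endpoints, with McNemar for the two binary endpoints and a linear mixed model for BCVA change. "The model will contain the variables for baseline BCVA, treatment groups (low dose and high dose), surgical group, eye (study eye vs fellow eye") and a treatment-by-eye interaction. Control is not named in either section.

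Appendix 5 (SAP 14.5), to which 10.2 refers, differs. Its comments say "treatment is coded as 1-high dose, 2-low dose, 0-control", and it has an ESTIMATE line labelled "control: study eye vs fellow eye". It has no line that subtracts the control difference from a treated one.

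On the choice of eye, SAP 3.1 says that with two eligible eyes the study eye "will generally be the worse eye affected", decided clinically. With one eligible eye, that eye is used. Protocol 7.1 adds that the subject's preference counts when the eyes are about equally affected. The 34-73 letter criterion (Protocol 8.1) applies to the study eye alone. The eye is fixed before randomisation (SAP 3.4), and both eyes are measured in all arms (SAP 3.1).

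**The concern.** The SAP calls the fellow eye a contralateral control. That reading requires the two eyes to be expected to change alike without treatment. Here one eye is selected, often for being worse and always for lying inside a BCVA window, while the other is whatever remains. If the selection uses the same noisy reading that serves as baseline, the selected eye tends to read higher on retest, which looks like benefit. McNemar's test does not correct for this, and a baseline covariate corrects only partly or overcorrects.

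The control arm has the same study/fellow designation, made by the same rule before randomisation, so it measures this selection effect without treatment. A treated-arm result reported without it could be read as confirming efficacy, or as failing to confirm it, for reasons unrelated to the vector.

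**Working it through.** **No plan figure to reproduce.** The documents give no expected size, power or error rate for the eye comparison, and no test-retest SD or between-eye SD. All sizes below rest on assumed values.

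**1. Selection drift by hand.** Let the true between-eye difference have SD t and each reading an error SD s. If both eyes qualify and the lower reading defines the study eye, the expected study-minus-fellow change with no true change is sqrt(2/pi) x 2s^2 / sqrt(t^2 + 2s^2), where sqrt(2/pi) = 0.798.
- s=3, t=10: 0.798 x 18 / sqrt(118) = 1.3 letters
- s=3, t=6: 0.798 x 18 / sqrt(54) = 2.0
- s=5, t=10: 0.798 x 50 / sqrt(150) = 3.3
- s=5, t=6: 0.798 x 50 / sqrt(86) = 4.3

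If the truly worse eye is chosen regardless of the reading, this term is zero.

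**2. What the baseline covariate does.** Adjusted difference = raw difference - slope x baseline gap. Both slope and gap are negative, so adjustment always lowers the study-eye advantage. It removes part of the drift in the first case and pushes below zero in the second.

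**3. Simulation, no treatment effect, one arm of 64.** Eligibility 34-73 for the study eye; two-eye model adjusted for baseline (without surgical group); exact two-sided McNemar. Assumed: true-change SD 4, ceiling 90 letters, one baseline reading. Settings are eye mean / eye SD / between-eye correlation / reading SD. The true between-eye difference SD is 15 x sqrt(2 x 0.3) = 11.6 or 20 x sqrt(2 x 0.5) = 20. The nominal rate is 2.5% per side.

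| Setting | Study eye is | Raw diff. | Model estimate | Model favours / against study eye | McNemar favours: >=15 / >=10 / <5 loss |
|---|---|---|---|---|---|
| 65/15/0.7/5 | lower reading | +2.76 | +1.75 | 21.1% / 0.1% | 3.0 / 15.7 / 22.6% |
| | truly worse | +0.51 | -0.66 | 1.3% / 7.3% | 0.7 / 2.4 / 2.5% |
| 75/15/0.7/3 | lower reading | +1.34 | +0.89 | 12.4% / 0.9% | 0 / 3.6 / 8.4% |
| | truly worse | +0.54 | -0.12 | 2.1% / 3.4% | 0 / 1.5 / 2.4% |
| 75/15/0.7/5 | lower reading | +3.24 | +2.00 | 25.6% / 0.1% | 5.6 / 26.1 / 25.9% |
| | truly worse | +1.40 | -0.28 | 1.7% / 5.6% | 1.7 / 6.6 / 5.1% |
| 60/20/0.5/3 | lower reading | +0.46 | +0.23 | 5.0% / 1.8% | 0 / 1.2 / 2.2% |
| | truly worse | -0.09 | -0.37 | 1.3% / 6.4% | 0 / 0.7 / 0.9% |
| 60/20/0.5/5 | lower reading | +1.13 | +0.51 | 5.3% / 0.9% | 0.9 / 5.3 / 3.9% |
| | truly worse | -0.31 | -1.02 | 0.6% / 12.2% | 0.3 / 1.3 / 0.6% |

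Check of step 2 on the first pair: the baseline gaps are 56.0 - 65.9 = -9.9 and 56.6 - 65.3 = -8.7, so the implied slopes are (2.76 - 1.75)/(-9.9) = -0.10 and (0.51 + 0.66)/(-8.7) = -0.13. Choosing at random between two eligible eyes still gave +0.1 to +1.1 letters in these five settings: the study-eye-only BCVA window contributes by itself.

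**4. Smaller between-eye spread.** With between-eye SD 6-10 and reading SD 3-5, the model shows about +0.5 to +3.3 letters (11-74% falsely favouring the study eye) on the lower reading, and about 0 to -1.5 letters on true severity.

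**5. Repeat baselines.** SAP 5.2 takes the median of repeated BCVA readings. With reading SD 3-5 and between-eye difference SD 6-12, choosing the lower baseline value gave 0.3-3.3 letters with one reading and 0.2-2.0 with a median of three.

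**6. The >=15-letter test.** Exact McNemar needs six discordant pairs all one way: 2 x 0.5^6 = 0.031, against 2 x 0.5^5 = 0.0625 for five. Across the full 18 scenarios (six settings by three selection rules), the rate favouring the study eye was 0-5.6%, above 2.5% in two. Under the plan's own assumption of no untreated responders it is 0%.

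**7. Subtracting control.** Comparing the study-minus-fellow change between a treated and a control arm of 64 each gave 4.4-5.6% false positives (nominal 5%, two-sided) in all 18 scenarios, and 3-7% in the step 4 settings, whichever way the within-arm bias ran.

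**The case against.** The strongest counter-argument concerns direction. A reader might infer that these analyses are biased towards treatment and tend to manufacture an effect. The documents do not support that. They describe a clinical judgement, with a one-eligible-eye rule and subject preference as exceptions, and never say that the lower screening reading decides. Most subjects come from the NIGHT study (Protocol 8), so earlier visits may inform the choice. Under selection on true severity, the adjusted model leans against the study eye. This objection stands: the sign is unknown.

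A reader might also infer that the control arm's eye difference goes unused. That is wrong for BCVA change, because Appendix 5 estimates it; it is right for McNemar. What stands is that text and code disagree and that neither forms the treated-minus-control contrast.

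The median-baseline rule helps only in part. Triplicate readings are required for subjects from outside NIGHT and for rollovers who differ by 10 letters or more from their last NIGHT visit; other rollovers are read once (Protocol 10.1).

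Finally, Fisher's test and the ANCOVA already compare study eyes across randomised arms, untouched by eye selection, and the eye analyses lie outside the hierarchy in SAP 10.3. That limits the importance, but it does not make the within-arm comparison a valid control.

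**Conclusion.** The design point holds. The within-arm eye comparisons do not have a reliable null, and the plan lacks the one contrast that would give them one. With no treatment effect, BCVA change can show roughly +0.5 to +3 letters for the study eye if it is picked on measured baseline BCVA (assumed reading SD 3-5, between-eye SD 6-10), less with median-of-three baselines or a wider between-eye spread, and nil or reversed if picked on true severity. The >=10-letter and <5-letter-loss McNemar tests can be materially inflated under the first rule (up to about 26% against 2.5%). For the >=15-letter test the effect is negligible to small.

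It would go too far to infer that the primary or key secondary conclusions are at risk: those rest on randomised study-eye comparisons. Severity is low. Confidence is high that the contrast is missing, and moderate on size and direction, because the selection rule and both SDs are absent from the documents.

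**What to change.** - Reconcile SAP 10.1 and 10.2 with Appendix 5 on which arms enter the eye model, and include control.
- Report as the main contrast, for each dose, (study minus fellow in that dose) minus (study minus fellow in control). Keep within-arm differences as description only.
- For the binary endpoints, tabulate the discordant pairs in all three arms and compare the paired difference, (pairs where only the study eye responds minus pairs where only the fellow eye responds) / n, between each dose and control, in place of McNemar within the treated arms alone.
- Check the Appendix 5 code. With treatment coded 0/1/2 and default numeric level ordering, control is the first level, so the line labelled high dose would return the control difference. The code also omits surgical group, which 10.2 includes.

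No new data are needed: the cost is SAP wording and one contrast per dose. The price is precision. With equal variances, the standard error rises by sqrt(1 + 64/64) = 1.41 for high dose (64 v 64) and by sqrt(1 + 32/64) = 1.22 for low dose (32 v 64), relative to the within-arm difference.
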